### **Primary Efficacy Endpoint**

Primary efficacy endpoint consists of 2 co-primary endpoints. Both co-primary endpoints will be analyzed using a Cochran-Mantel-Haenszel test adjusted for the randomized stratification variables (IGA severity and PP NRS) for both populations (baseline PP NRS  $\geq 4$ ; baseline PP NRS  $\geq 7$ ) to compare the proportion of subjects achieving success between treatment groups. The estimate of treatment difference, the corresponding 2-sided 95% confidence interval, and p-values will be presented.

Any subjects with missing data at Week 16 will be regarded as a non-responder. If a subject received any rescue therapy, the data after receipt of rescue therapy will be set to missing and subsequently regarded as a non-responder for the respective primary endpoint.

CONFIDENTIAL

### **Key Secondary Efficacy Endpoints**

All key secondary endpoints will be analyzed similar to the analysis of primary endpoint using a stratified Cochran-Mantel-Haenszel test.

### **Multiplicity Adjustment for Two Co-Primary and Key Secondary Efficacy Endpoints**

The primary comparison of interest is nemolizumab 30 mg compared to placebo for the co-primary endpoints in both populations (baseline PP NRS  $\geq 4$ ; baseline PP NRS  $\geq 7$ ).

To control the type I error at 5% significance level, a serial gatekeeping approach will be implemented. The co-primary endpoints will be tested at 2.5% significance level for each population. If both co-primary endpoints are statistically significant at 2.5% significance level, the key secondary endpoints will be tested sequentially following hierarchical testing procedure using the pre-specified order of endpoints in Section 7.4 for each population. The comparisons for key secondary endpoints will be made sequentially, and the subsequent tests will stop when no statistical difference is found.

[figure not shown]
Other secondary endpoint comparisons will not be adjusted for multiplicity.

CCI

CONFIDENTIAL

[figure not shown]

CCI

CONFIDENTIAL

CCI

#### **10.1.4 Safety Variables**

All safety analyses will be based on the safety population.

Summary of all safety endpoints will be presented by study period (initial treatment period, maintenance period, and follow-up period) for each treatment group.

##### **10.1.4.1 Extent of Exposure**

The duration of exposure and the number of subjects exposed to study medication will be summarized by treatment group and visit. The number of subjects exposed will be presented by study periods (initial treatment period and maintenance period).

CONFIDENTIAL

#### **10.1.4.2 Adverse Events**

Treatment-emergent AEs, defined as those AEs occurring after the first administration of study treatment until the last study visit, will be tabulated in frequency tables by system organ class and preferred term based on the Medical Dictionary for Regulatory Activities for each study phase. Additional summary tables will be provided for SAEs, AEs related to the study drug(s) (reasonable possibility, no reasonable possibility), AEs related to the study procedure, AESIs, and AEs leading to treatment discontinuation and study withdrawal. For a given AE, a subject will be counted once even if he/she has experienced multiple episodes of that particular AE.

Pretreatment AEs will be listed separately.

#### **10.1.4.3 Clinical Laboratory**

Laboratory data (absolute values and change from baseline) will be summarized by visit and treatment group for each study phase. In addition, the number and percentage of subjects below, within, and above the laboratory reference ranges and the number and percentage of subjects who met criteria of potential clinically significant value will be summarized by treatment group. Shift tables will be generated using the reference ranges. Reference ranges will be provided in the laboratory manual.

Abnormal laboratory values from tests on baseline visit will not be considered as TEAEs, as the sample collection will be conducted before study drug administration.

#### **10.1.4.4 Vital Signs**

All vital signs and weight data (absolute values and change from baseline) will be summarized by visit and treatment group. In addition, the number and percent of subjects with clinically significant abnormal values (of clinical concern as identified by the investigator) will be summarized by treatment group.

#### **10.1.4.5 Peak Expiratory Flow**

The PEF measurements (absolute values and change from baseline) will be summarized by visit, treatment group, and medical history of asthma.

Further details on safety analyses will be provided in the SAP.

[figure not shown]
CONFIDENTIAL

#### 10.1.4.6 Physical Examination

The number and percentage of subjects who are normal, abnormal (clinically significant [CS]), and abnormal (not clinically significant [NCS]) will be displayed by treatment at each visit.

#### 10.1.4.7 Electrocardiogram

The number and percentage of subjects who have ECGs that are abnormal/CS and normal/NCS will be displayed by treatment at each visit.

#### 10.1.7 Psychometric Validation Analyses

Psychometric analyses will be conducted on the Phase 3 data for the evaluation of the PP NRS, CCI in both adult and adolescent subjects. These blinded analyses will be performed by the designated CRO after approximately half of adult and adolescent subjects complete the initial treatment period, on the basis of a separate psychometric validation statistical analysis plan.

CONFIDENTIAL

### 10.1.8 Interim Analyses

No interim analysis is planned.

**Week 16 Analysis:** Primary analysis may be carried out once all subjects have completed the Week 16 visit or have withdrawn from the study. No personnel directly involved with the conduct of the study shall have access to the unblinded data before the completion of the trial in order to avoid introducing bias to the remaining study data.

### 10.1.9 Handling of Missing Data

The primary method to impute the missing values will be as follows:

**Continuous Endpoints:** For continuous endpoints during initial period, the MI under MAR assumption approach and the MMRM approach will be used to handle the missing data for the selected secondary endpoints. QoL endpoints (eg, DLQI/cDLQI, EQ-5D, PIQ) may be imputed using last observation carried forward (LOCF), where applicable.

**Binary Endpoints:** All missing values will be treated as a non-responder for the binary endpoints. To assess the robustness of non-responder analysis, a tipping point analysis will be performed. The MI under MAR assumption, LOCF, and OC will be used as sensitivity analysis to impute the missing values for the primary and key secondary endpoints.

**Use of rescue therapy:** All efficacy data, except OC, will be set to missing after rescue medication is used. In OC analysis, no observed data after subject has received rescue treatment will be excluded. There will be no imputations for missing data.

### 10.1.10 Sensitivity Analyses for Primary and Key Secondary Endpoints

The following sensitivity analyses will be conducted for the robustness of the analyses.

- Same analysis on Per-protocol population
- **Tipping point analysis** will be performed by converting non-responders due to missing data to responders in successive increments ( $\Delta$ ) for both treatment groups to assess the robustness of analysis. The value of  $\Delta$  that overturns (ie, non-significant) the primary results will represent the tipping point. A graphic display of all possible combination of the number of responders among both treatment groups will be

CONFIDENTIAL

presented.

- **Multiple imputation (MI) methods** for missing data: The MI imputation will be carried out as follows.
  1. Imputation Phase
    - a. A 50 imputed datasets with a monotone missing pattern will be created using SAS MI procedure based on the observed data (Markov-Chain-Monte-Carlo method, MCMC). The seed to be used is 118169 (the Protocol number). Pattern of missing data will be evaluated and it is expected that the pattern of missing data will be monotonic. For non-monotone missing data patterns, MCMC method of MI procedure will be used to impute enough data so that the remaining missing data is monotone.
    - b. Each of the imputed datasets will be used to generate 50 complete datasets, using the following approaches:
      - i. *Ordinal data (eg, IGA score)*: A logistic regression method to impute the ordinal missing data, including treatment, randomization strata, and assessments from earlier time points as covariates. Response or total score of the subjects will be derived using these imputed data.
      - ii. *Continuous data (eg, EASI score)*: A linear regression model including treatment, randomization strata, and assessments from earlier time points as covariates will be used to impute the score. Response or total score of the subjects will be derived using these imputed data.
  2. Analysis Phase: The analysis will be conducted using the complete datasets.
    - a. *Binary endpoint*: The complete datasets will be modelled for the endpoint using CMH method as per analysis described in Section 10.1.3 . Proportion of responders in each treatment arm, difference and standard error will be calculated.
    - b. *Continuous endpoint*: The complete datasets will be analysed using ANCOVA including treatment group and randomization stratification factors as factors and appropriate baseline values as a covariate, if applicable. LSMeans in each treatment arm, difference and standard errors will be calculated.
  3. Pooling Phase: The results from the analysis phase will be combined as follows.
    - a. *Binary endpoint*: The results from the CMH analysis of the multiple imputed datasets will be combined using the Rubin (1987) and Li et al (1991) approach to produce pooled CMH statistics and p-value. Proportion

CONFIDENTIAL

of responders in each treatment arm, difference and standard error will be combined using the MIANALYZE procedure in SAS.

- b. *Continuous endpoint*: The LSMeans in each treatment arm, difference and standard errors from the ANCOVA of the multiple imputed datasets will be combined using the MIANALYZE procedure in SAS.

- **Last Observation Carried Forward (LOCF)** imputation method for missing data (or where rescue medication is received)
- **Observed Case (OC)** - No data will be imputed. For this analysis, if any rescue medication is received, and data are collected post rescue receipt, data post-rescue will be analyzed as observed (ie, not set to missing).

Sensitivity analyses may be performed to evaluate the impact COVID-19 deviations. Further details will be provided in SAP.

## 10.2 Determination of Sample Size

To achieve at least 90% power for each co-primary endpoint at 2.5% significance level, 150 subjects per group will be required to detect the following differences between treatment groups for 2 co-primary endpoints with 2:1 randomization ratio, assuming 15% dropout rate during the initial treatment period.

With 2:1 randomization, 180 subjects in nemolizumab and 90 subjects in placebo will be required to detect the differences in both co-primaries to achieve 90% power.

*IGA Success*: To detect a difference of 18%, assuming IGA response for nemolizumab 30% and placebo 12% at Week 16.

*EASI-75 Response*: To detect a difference of 30%, assuming EASI-75 response for nemolizumab 49% and placebo 19% at Week 16.

To ensure sufficient exposure with nemolizumab and to ensure sufficient size of safety database, sample size is increased to 750 subjects in total with a randomization ratio of 2:1. This sample size will provide more than 99% power to detect the treatment difference for both co-primary endpoints at 2.5% significance level.

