To control the type I error at 5% significance level, a serial gatekeeping approach will be implemented. The co-primary endpoints will be tested at 2.5% significance level for each population. If both co-primary endpoints are statistically significant at 2.5% significance level, the key secondary endpoints will be tested sequentially following hierarchical testing procedure using the pre-specified order of endpoints for each population. The comparisons for key secondary endpoints will be made sequentially, and the subsequent tests will be stopped when no statistical difference is found.

Other secondary endpoint comparisons will not be adjusted for multiplicity.

Sample Size

To achieve at least 90% power for both co-primary endpoints at 2.5% significance level, 150 subjects per group will be required to detect the following differences between treatment groups for 2 co-primary endpoints with 1:1 randomization ratio, assuming 15% dropout rate during the initial treatment period.

With a 2:1 randomization, 180 subjects in nemolizumab and 90 subjects in placebo will be required to detect the differences in both co-primary endpoints to achieve 90% power.

[figure not shown]
*IGA Success:* To detect a difference of 18%, assuming IGA response for nemolizumab 30% and placebo 12% at Week 16.

*EASI-75 Response:* To detect a difference of 30%, assuming EASI-75 response for nemolizumab 49% and placebo 19% at Week 16.

CONFIDENTIAL

To ensure sufficient exposure with nemolizumab and to ensure sufficient size of the safety database, the sample size is increased to 750 subjects in total with randomization ratio 2:1. This sample size will provide more than 99% power to detect the treatment difference for both co-primary endpoints at 2.5% significance level.

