### 6.2.3 Phase 2b Dose-Ranging Study

The phase 2b study was a randomized, placebo-controlled, double-blind, parallel-group, dose-ranging study to evaluate the efficacy and safety of various doses of nemolizumab in moderate-to-severe AD subjects with severe pruritus (peak pruritus numeric rating scale [PP NRS]  $\geq 7$ ).

A total of 226 adult subjects were randomized (1 subject in the placebo group was randomized but not treated): 57 subjects were randomized to placebo and 169 subjects were randomized to nemolizumab arms (55 subjects to 10 mg, 57 subjects to 30 mg, and 57 subjects to 90 mg). There were 176 subjects (77.9%) who completed the treatment and 44 subjects (19.5%) who discontinued the study. Overall, all demographic and baseline disease characteristics were similar in all treatment groups.

At the Week 24 visit, a greater percent change reduction in Eczema Area and Severity Index (EASI) was observed with the nemolizumab 30-mg dose (least squares mean difference vs placebo = 16.7%) and the difference was statistically significant (95% confidence interval [CI] = -30.2, -3.2;  $p < 0.05$ ) compared to placebo. The nemolizumab 10-mg dose showed marginally significant difference vs placebo (least squares mean difference = 13.6%; 95% CI = -27.3, 0.0;  $p = 0.05$ ). However, the difference between the nemolizumab 90-mg dose and placebo did not achieve statistical significance.

The secondary endpoint of Investigator's Global Assessment (IGA) success (clear/almost clear and 2-point reduction) was not statistically significant at Week 24 (25.5% in nemolizumab 10 mg, 36.8% in 30 mg, 22.8% in 90 mg, and 21.1% in placebo). However, the difference was statistically different for the 30-mg dose compared to placebo at Week 16 (33.3% vs 12.3%;  $p = 0.008$ ). The PP NRS responder (PP NRS improvement  $\geq 4$ ) rate was statistically significant ( $p < 0.05$ ) for the nemolizumab 10-mg and 30-mg doses at Week 24, and all nemolizumab doses were statistically significantly superior to placebo at Week 16 ( $p < 0.05$ ). Nemolizumab demonstrated an early onset of action in pruritus as early as Week 1. In addition, the proportion of EASI-75 responders was statistically significantly greater for nemolizumab 30 mg at Week 24 and for both the 30-mg and 90-mg doses at Week 16 compared to placebo ( $p < 0.05$ ). The sleep disturbance NRS was highly statistically significant for all 3 nemolizumab doses at Week 24 ( $p < 0.001$ ) vs placebo.

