#### Initial Treatment Period (Baseline/Day 1 to Week 16 Pre-dose)

The initial treatment period is defined as Day 1/baseline through Week 16 (before the Week 16 dose, with last dose at Week 12). Approximately 750 total subjects will be randomized (2:1) to receive either nemolizumab (CD14152) or placebo, stratified by baseline disease severity (IGA; moderate: IGA = 3; severe: IGA = 4) and PP NRS severity [PP NRS  $\geq$  7; PP NRS < 7). A minimum of 250 subjects will be randomized in each PP NRS strata. [Table 4](#) summarizes study drug dosing during the initial treatment period.

CONFIDENTIAL

Subjects will continue to use background topical therapy, which should be adjusted according to the disease activity and tolerability, including tapering when signs and symptoms improve, discontinuation when lesions clear, and restarting if signs and symptoms recur, based on investigator clinical judgment. Any adjustments to background topical therapy are to be recorded in the appropriate case report form (CRF).

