4.3. Determination of Sample Size

With a 2:1 randomization, 180 subjects in nemolizumab and 90 subjects in placebo required to detect the differences in both co-primary endpoints to achieve 90% power.

IGA Success: To detect a difference of 18%, assuming IGA response for nemolizumab 30% and placebo 12% at Week 16.

EASI-75 Response: To detect a difference of 30%, assuming EASI-75 response for nemolizumab 49% and placebo 19% at Week 16.

To ensure sufficient exposure with nemolizumab and to ensure sufficient size of the safety database, the sample size increased to 750 subjects in total with randomization ratio 2:1. This sample size will provide more than 99% power to detect the treatment difference for both co-primary endpoints at 2.5% significance level.

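### The >99% power figure names no population: it holds for all 750 subjects, but the separate PP NRS ≥7 co-primary test is guaranteed only 250, fewer than the 270 the plan says 90% power needs

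*Protocol*

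**What the plan says.** - **Protocol 10.2** assumes IGA success of 30% v 12%, EASI-75 of 49% v 19%, and 15% dropout. It says "150 subjects per group will be required to detect the following differences between treatment groups for 2 co-primary endpoints with 2:1 randomization ratio", and then that "180 subjects in nemolizumab and 90 subjects in placebo will be required to detect the differences" with 90% power. It raises the total to 750 for exposure and the safety database and ends: "This sample size will provide more than 99% power to detect the treatment difference for both co-primary endpoints at 2.5% significance level". No sentence names a population.
- **Protocol synopsis, Sample Size**, gives the same 150 per group "with 1:1 randomization ratio, assuming 15% dropout rate during the initial treatment period".
- **SAP 4.3** keeps "180 subjects in nemolizumab and 90 subjects in placebo required to detect the differences in both co-primary endpoints to achieve 90% power", repeats >99%, and states no dropout rate.
- **Protocol 10.1.3, Multiplicity Adjustment**: "The co-primary endpoints will be tested at 2.5% significance level for each population". The populations are all subjects (baseline PP NRS ≥4) and baseline PP NRS ≥7. SAP 10.1.1 makes the tests two-sided and, in PP NRS ≥7, uses a CMH test stratified by IGA severity only. SAP 10 lets the second population be tested at 5%, but only after every co-primary and key secondary endpoint has passed in the first.
- **Protocol 8.1**: "A minimum of 250 subjects will be randomized in each PP NRS strata". This is the only control on the size of the PP NRS ≥7 population.
- **Protocol 8.1, Maintenance Period**, defines a responder as IGA 0/1 or EASI-75, yet forecasts 190 + 26 subjects from responder rates of 45% and 12%.

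**The concern.** Two populations carry a primary claim, and each has its own alpha and its own key secondary hierarchy. Only one power figure is given, and a reader would take it to cover both. The guaranteed size of the second population is below the plan's own requirement for 90% power, before any formula is applied.

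The requirement itself looks doubtful. The 1:1 total is 300 with dropout, while the 2:1 total for the same power and assumptions is 270. Unequal allocation would not be expected to need fewer subjects here.

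At stake is how well the PP NRS ≥7 claim is protected against a false negative on IGA success, and whether the published sample size derivation can be reproduced.

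**Working it through.** **Inputs.** IGA 30% v 12%, EASI-75 49% v 19%, 15% dropout, 750 subjects at 2:1 (Protocol 10.2); two-sided 2.5% (SAP 10.1.1), so z = 2.2414; 250 to 500 subjects with PP NRS ≥7 (Protocol 8.1: at least 250 in each stratum of 750).

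**Formulas.** With p̄ the weighted mean rate, s0 = √[p̄(1−p̄)(1/n1+1/n2)] and s1 = √[p1(1−p1)/n1 + p2(1−p2)/n2]:
- pooled power = Φ[(|p1−p2| − z·s0)/s1]
- unpooled power = Φ[|p1−p2|/s1 − z]
- arcsine power = Φ[(2asin√p1 − 2asin√p2)/√(1/n1+1/n2) − z]

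The power of the Pearson chi-square test was also computed by exact binomial enumeration. Dropout is shown two ways: sample size × 0.85, and both rates × 0.85 (missing as non-response).

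**1. The plan's figure, 500:250.** p̄ = 0.24, s0 = 0.03308, s1 = 0.02902. (0.18 − 2.2414 × 0.03308)/0.02902 = 3.65, so IGA power is 99.99% (99.9% with dropout either way). EASI-75 exceeds 99.99%. The >99% statement is right for 750.

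**2. PP NRS ≥7 at the minimum, 167:83.** p̄ = 0.24024, s0 = 0.05738, s1 = 0.05030. (0.18 − 2.2414 × 0.05738)/0.05030 = 1.02, so IGA power is 84.7%.

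| IGA power, 167:83 | No further dropout | n × 0.85 | Rates × 0.85 |
|---|---|---|---|
| Pooled | 84.7% | 77.1% | 74.8% |
| Exact chi-square | 85.4% | 77.9% | 76.0% |
| Arcsine | 86.9% | 80.5% | 78.8% |
| Unpooled | 90.9% | 85.5% | 83.9% |
| Pooled, phase 2b rates 33.3% v 12.3% | 93% | 88% | 86% |
| Pooled, 30% v 12%, alpha 5% (recycled) | 91% | 86% | 84% |

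EASI-75 (pooled) is 99.6%, 98.8% and 97.9%, so IGA determines joint power. A simulated stratified CMH test gave 86.6%, and 79.9% with 15% fewer subjects. It assumed a 70/30 split of IGA 3 and 4 with rates of 36/15 and 16/5, which average to 30/12. The most favourable combination (phase 2b rates, 5% alpha, no dropout) gives 96.7% pooled and 98.4% unpooled, so no variant checked reaches 99% at the minimum.

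**3. Larger PP NRS ≥7 populations (pooled).** At 375 subjects: 97%, or 92–93% with dropout. At the maximum of 500: 99.4%, or 98% with dropout.

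**4. The 180:90 requirement.**

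| IGA power, 180:90 | No further dropout | n × 0.85 | Rates × 0.85 |
|---|---|---|---|
| Pooled | 87.8% | 81.0% | 78.8% |
| Exact chi-square | 88.5% | 81.8% | 79.9% |
| Arcsine | 89.6% | 83.8% | 82.2% |
| Unpooled | 93.1% | 88.3% | 86.8% |

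Total needed for 90% power:

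| Formula | 1:1 evaluable | 2:1 evaluable | 2:1 randomized (÷ 0.85) |
|---|---|---|---|
| Pooled | 250 | 288 | 339 |
| Arcsine | 243 | 274 | 322 |
| Unpooled | 242 | 243 | 286 |

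The 1:1 figure reproduces with dropout: 125/0.85 = 147.1, so 148 per group, stated as 150. No formula gives a smaller total at 2:1 than at 1:1, and every randomized 2:1 total exceeds 270.

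**5. The ratio label.** Protocol 10.2 attaches 150 per group to 2:1 and the synopsis attaches it to 1:1. Equal groups are 1:1.

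**6. Maintenance forecast.** 500 × 0.85 × 0.45 = 191.3 and 250 × 0.85 × 0.12 = 25.5 reproduce 190 + 26. EASI-75 alone makes a subject a responder, so the rates cannot be below the assumed 49% and 19%: 500 × 0.85 × 0.49 = 208.3 and 250 × 0.85 × 0.19 = 40.4, about 248 in total as a lower bound.

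**The case against.** - **The >99% sentence follows directly on the increase to 750 and is correct for 750.** That stands. On this part the fault is a missing second figure, not a wrong first one.
- **250 is a floor, not a forecast.** This stands too. It is reached only if 500 of the 750 subjects have PP NRS <7. But the plan gives no expected split, so the floor is the only size a reader can rely on.
- **The lower figures may count dropout twice.** The phase 2b rates equal 19/57 and 7/57, that is, all randomized subjects. If 30% v 12% follows that convention, dropout is already included and the 75–78% branch falls away. The plan does not say, so both branches need to be shown.
- **The planned test is a stratified CMH, which does slightly better than the pooled formula.** True: 86.6% against 84.7% under the assumed strata. The difference is small and does not bring the floor to 90%.
- **270 may be an evaluable count, where arcsine (89.6%) and unpooled (93.1%) roughly support 90%.** This is possible, but the text gives no such label and the sentence before it includes dropout. On that reading the randomized requirement rises to 318 (270/0.85) and the shortfall at 250 grows.
- **The maintenance forecast is operational and its endpoints are only summarized descriptively.** Agreed. It is a secondary point, and no test depends on it.

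**Conclusion.** The concern holds. The >99% figure is correct for the full population, and that test is not affected. For PP NRS ≥7, a second primary population, no power is stated. At the permitted minimum of 250, IGA power is about 85% by the pooled or chi-square test (about 87% by arcsine or the illustrative CMH, 91% unpooled) if 30% v 12% already counts missing as failure. If it does not, pooled or chi-square power is about 75–78%. These figures assume that the planning rates apply in PP NRS ≥7; the phase 2b rates give 93% at the floor before further dropout.

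Three stated items also need correction. The 180:90 requirement does not give 90% power under any formula checked once the plan's 15% dropout is applied. The ratio attached to 150 per group in Protocol 10.2 contradicts the synopsis. The maintenance responder rates fall below the minimum implied by their definition. The sample size text should be corrected; the success of the trial as a whole does not depend on it.

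**What to change.** Restate Protocol 10.2, the synopsis and SAP 4.3 as follows.

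1. Label >99% as the full population, n = 750.
2. Add PP NRS ≥7 power at the minimum of 250 and at the expected stratum size. Name the test formula and the dropout assumption, and say whether 30% v 12% already counts missing as non-response. For example: *at the minimum of 250, IGA power is about 85% if missing data are already counted in 30%/12%, and about 75–78% if not (pooled-variance or chi-square test)*. A figure for the planned CMH test could be given beside it, with its stratum assumptions.
3. Either restate the 2:1 requirement with its method (pooled: 288 evaluable, 339 randomized with 15% dropout) or restate the power that 180:90 provides. Label 150 per group as 1:1.
4. Reconcile the maintenance forecast with the responder definition: at 49% and 19% with the same 0.85 factor, at least about 208 nemolizumab and 40 placebo subjects.

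The cost is wording only. No subjects are added and no analysis changes. The downside is a less favourable stated power for one of the two primary populations.
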